### 11 QUALITY CONTROL AND ASSURANCE

The study will be initiated and conducted under the Sponsorship of BBI. The clinical supplies of BBI608 and CRFs will be supplied by BBI or its representative. Representatives of BBI will monitor the study to verify study data, medical records, and CRFs in accordance with current ICH GCPs and other applicable regulations and guidelines.

### 11.1 Compliance with the Protocol

The Investigator will notify the Sponsor of any deviations from the protocol. Such contact with the Sponsor will be made as soon as possible to permit a decision as to whether or not the subject (for whom the deviation from the protocol was effected) is to continue in the study. The case records will describe the deviation from the protocol and state the grounds for it.

### 11.2 Registration and Enrollment

This is an open-label, non-randomized study. Boston Biomedical should be notified as soon as a subject qualifies for entry in the protocol. Subjects will be registered by faxing Boston Biomedical or their designee, within 7 days prior to the 1st drug administration. At that time the combination arm will be assigned. The subject will be enrolled into the study when the subject receives the 1st dose of study drug. Registration and enrollment forms and faxing instructions will be provided with the case report forms (CRFs). The site should maintain a log of all subjects who are screened but do not qualify for the study or who do not receive study drug. The reason for disqualification should be noted in the log.

### 11.3 Removal, Replacement, or Early Withdrawals of Subjects

If a subject exits the study prior to receiving four weeks of BBI608 or does not receive four weeks of BBI608 for a reason other than DLT, an additional subject may be recruited to replace the subject.

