### **5.4** Tumor Evaluation Visits

Disease status and tumor response will be assessed in eight-week intervals up to one year after starting therapy (calculated from the first dose of BBI608) or as clinically indicated. Standard

imaging studies should be performed according to institutional procedures. Tumor response for solid tumors will be evaluated using the guidelines for Response Evaluation Criteria in Solid Tumors (RECIST 1.1) outlined in Section 9.

Once progression of disease during therapy is documented, patients must be taken off treatment and may receive any therapy as determined by their treating physician.

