## 5.6 Discontinuation from Study

Patients will be removed from the study at any time if they meet any of the following criteria:

- Documented radiologic or clinical progression of disease
- Noncompliance with any part of the study, as evaluated by the Principal Investigator and Medical Monitor
- Withdrawal of consent
- Lost to Follow-up
- Death
- Clinically unacceptable toxicities despite optimal treatment.

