### Simon two-stage design for Phase II

	Patient number									
Combo Therapy	Stage 1	Stage 2	Total*							
Cetuximab	8	16	24							
Panitumumab	8	16	24							
Capecitabine	6	12	18							

\*If any of the three arms reach a DCR of 60% or more at the end of Simon Stage 2, a one-time option to expand accrual to a total sample size of up to 50 patients may be implemented for each arm.

For the Cetuximab and Panitumumab combination cohorts, if the disease control rate in stage 1 reaches 3 of 8 or above, additional patients will be enrolled into the stage 2 cohort. For the Capecitabine combination cohort, if the disease control rate in stage 1 reaches 2 of 6 or above, additional patients will be enrolled into the stage 2 cohort.

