### 10.3 Analysis Populations

All patients receiving at least one dose of BBI608 will be considered evaluable for safety analysis. Adverse event incidence rates will be described by the frequency of adverse events, categorized by NCI CTCAE. Listings of laboratory test results collected at baseline and during the study will be generated. Descriptive statistics summarizing the changes in those laboratory tests over time will be presented.

Patients who have received at least one cycle of study treatment and have had at least one disease assessment following the initiation of therapy will be considered evaluable for disease control rate and overall response. Progression-free survival and overall survival will be evaluated in the intent-to-treat population. Anti-tumor activity will be evaluated on an exploratory basis and will be summarized using descriptive statistics or graphics.

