### 10.4 Efficacy

The primary population for the efficacy evaluation will be the evaluable population, defined as patients who have been treated with at least 80 % of 1 complete cycle of BBI608 and a combination drug. The primary efficacy outcome measure will be disease control rate, defined as the proportion of patients with a documented complete response, partial response and stable disease (CR + PR + SD) based on RECIST. In addition, progression-free survival (PFS) and overall survival (OS) will be obtained from intent-to-treat patients. PFS will be calculated from the date of patient enrolment into the trial until documented disease progression based on RECIST. OS will be calculated from the date of patient enrolment into the trial until death.

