6.3. Response Evaluable Set

The response evaluable set is defined as patients who have received at least one cycle of study treatment unless discontinued early due to death or PD and have had at least one disease assessment following the initiation of therapy. At least one cycle of study treatment is defined as at least 80% daily treatment compliance at targeted dose level during one cycle (cycle 1 or cycle 2) period prior to the first post-dosing imaging assessment. The response evaluable set will be used for analyses of disease control rate and overall response.

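### Protocol 10.3 and 10.4 leave early progressions and deaths out of the primary DCR, so DCR reads too high; SAP 6.3 closes only part of the gap

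*Protocol*

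**What the plan says.** Two protocol sections define who counts towards DCR. Section 10.3 treats as evaluable: "Patients who have received at least one cycle of study treatment and have had at least one disease assessment following the initiation of therapy". Section 10.4 names the primary efficacy population as "patients who have been treated with at least 80 % of 1 complete cycle of BBI608 and a combination drug". Neither makes an exception for a patient who progressed or died before reaching that point.

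Section 11.3 deals with replacement. If a subject exits before the four-week mark, or otherwise "does not receive four weeks of BBI608 for a reason other than DLT, an additional subject may be recruited to replace the subject". Section 5.6 lists reasons for removal from the study; the first is "Documented radiologic or clinical progression of disease", and death is also on the list.

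For cetuximab and panitumumab, section 10.2 continues to stage 2 "if the disease control rate in stage 1 reaches 3 of 8 or above". For capecitabine the rule is 2 of 6. A DCR of 60% at the end of stage 2 opens the option to expand. No denominator is named for any of these rules.

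The SAP differs. Section 6.3 defines the response evaluable set as "patients who have received at least one cycle of study treatment unless discontinued early due to death or PD", and then also requires at least one disease assessment after the start of therapy. Section 8.2.2 reports the primary DCR in that set and adds a sensitivity analysis in the safety set. Section 4.2.2 states that the Simon decision rule was not applied.

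**The concern.** A patient who progresses or dies in week 2 or 3 is a plain failure of disease control. Under protocol 10.3 and 10.4 that patient is not evaluable and so does not enter the primary DCR. Under 11.3 another patient may be recruited in that place. What remains is DCR among patients who got through roughly the first four weeks, and removing failures alone can only raise it.

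At stake is the primary endpoint, and for the protocol as written also the stage-1 gate and the expansion trigger. The protocol and the SAP would also give different DCRs for the same patients, because the SAP keeps some early failures that the protocol excludes.

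**Working it through.** **Inputs.** Null and target DCR are 30% and 60% for cetuximab and panitumumab, and 15% and 60% for capecitabine (protocol 10.2). Alpha is 5%, one-sided (synopsis), and power is 80%. Stage sizes are 8 + 16 = 24 and 6 + 12 = 18. The documents do not give the early-failure share f; 10% and 20% are used as assumptions.

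**The plan's own sample size.** A search over two-stage designs for 30% against 60% gives Simon's optimal design as 8 then 24, with type I error 4.6% and power 80.6%. The stated 8 and 24 therefore reproduce. That design continues at 4 of 8 and succeeds at 11 of 24, whereas the protocol continues at 3 of 8 and states no final cut. With 3 of 8, a cut of 11/24 gives an error of 6.5%. The smallest cut that keeps it at or below 5% is 12/24 (error 2.9%, power 86.1%), and that derived cut is used below. For capecitabine with 2 of 6, the corresponding cut is 6/18 (error 3.1%, power 95.6%).

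**Who is lost.** Section 10.4 requires 0.80 × 28 = 22.4 days of treatment; 10.3 requires a full cycle and a scan. A patient leaving between about day 23 and day 27 can count under 10.4 but fails 10.3 and is replaceable under 11.3, so the two sections also differ from each other.

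**Effect on DCR.** If p is the DCR among all treated patients and a share f are early failures outside the denominator, then

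DCR among those counted = p / (1 - f).

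- p = 30%: 0.30/0.90 = 33.3%; 0.30/0.80 = 37.5%.
- p = 15%: 0.15/0.90 = 16.7%; 0.15/0.80 = 18.8%.
- An observed 60% corresponds to 0.60 × 0.90 = 54% or 0.60 × 0.80 = 48% of all treated.

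In small numbers: 11 treated, 3 early progressors replaced, 3 of the other 8 controlled. The protocol reads 3/8 = 37.5%; all treated gives 3/11 = 27%.

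**Effect on the protocol's rules**, if evaluable patients are the denominator and their number is made up to 8, 24, 6 or 18. With q = p/(1-f), the gate is P(X ≥ 3), X ~ Bin(8, q). At q = 0.30 this is 1 - (0.0576 + 0.1977 + 0.2965) = 0.448. The two-stage figure sums P(X = x) × P(Y ≥ cut - x) over continuing x, with Y the stage-2 count.

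| Arm, true DCR | Quantity | f = 0 | f = 10% | f = 20% |
|---|---|---|---|---|
| Cetuximab/panitumumab, 30% | Pass 3 of 8 | 45% | 53% | 63% |
| | Pass 3/8, then 12/24 | 2.9% | 6.3% | 13.6% |
| | Pass 3/8, then 15/24 (60% trigger) | 0.1% | 0.3% | 1.1% |
| Capecitabine, 15% | Pass 2 of 6 | 22% | 26% | 31% |
| | Pass 2/6, then 6/18 | 3.1% | 4.8% | 7.7% |

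**What the SAP recovers.** SAP 6.3 keeps early progression or death only when there is a post-baseline assessment. Protocol 5.4 says: "Disease status and tumor response will be assessed in eight-week intervals up to one year after starting therapy". A patient leaving within four weeks has therefore had no scheduled on-treatment scan. The end-of-study visit includes tumor measurement, but the schedule of assessments waives it if CT or MRI was done in the last four weeks, and a baseline scan can meet that condition. Early deaths and clinical progressions without a scan stay out of the primary DCR. SAP 6.3 has no waiver for early exits due to toxicity.

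**The case against.** The strongest objection concerns 11.3. A reader might infer that the replacement rule itself removes failures from the analysis. It does not: it says that a further subject may be recruited, and its four-week and DLT wording fits the 28-day DLT window. The exclusion comes from 10.3 and 10.4. Without 11.3 the expected DCR among evaluable patients would be the same. This stands, and the repair belongs mainly in the population definitions.

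A reader might also infer that inactive arms were carried forward in this trial. The documents do not support that. SAP 4.2.2 says that no Simon rule was applied, SAP 4.1 has no hypothesis testing, and protocol 10.1 plans no formal analysis. The denominator for 3 of 8, 2 of 6 and 60% is implied, not stated, and 12/24 is derived. At the one end-of-stage-2 threshold that the protocol does state, 60%, the error stays near 1% even at f = 20%.

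Nor can f be bounded from the phase I data in protocol 1.4, where 13 of 22 colorectal patients were evaluable and DCR was 8/13 = 62% (8/22 = 36% of those enrolled). That was monotherapy in another trial, with no reasons given for the other 9. It shows that the denominator matters, not how much it matters here.

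Finally, the SAP already plans a safety-set DCR, and an early progressor who is scanned at the end-of-study visit is kept. Both reduce the problem in the final analysis. They do not remove it. The safety-set result is a sensitivity analysis. Appendix 1.2 classes early death and absence of any post-baseline assessment as NE, and the overview table in SAP 8.2.3.3 handles response data as observed cases. Applying that analysis to all safety-set patients suggests that NE patients stay in the denominator, but nothing says that they count as not controlled.

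**Conclusion.** The point holds for the definition of the DCR population. Under protocol 10.3 and 10.4, early treatment failures leave the denominator and DCR is overstated by the factor 1/(1-f): 30% reads as 33% at f = 10% and 37.5% at f = 20%. The direction is certain; the size depends on an f that the documents do not give.

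SAP 6.3 contradicts the protocol by retaining early progression or death, yet still loses those never scanned. The gate figures (45% to 53% and 63%; two-stage error 2.9% to 6.3% and 13.6%) rest on evaluable patients as the implied denominator and on the derived 12/24 cut. They describe the protocol as written, not decisions taken in the trial.

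**What to change.** - **Protocol 10.3 and 10.4, and SAP 6.3:** state that treated patients who stop early for progression, death or toxicity count as not controlled in the DCR, whether or not they were scanned. Use one definition in all three places.
- **SAP 8.2.2:** state that NE counts as not controlled in the safety-set DCR, and report that DCR beside the evaluable-set DCR.
- **Protocol 11.3:** state that a replacement fills the six-patient DLT count only and does not remove the replaced patient from any DCR count.

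If the protocol can no longer be amended, the SAP changes alone settle how the reported DCR is calculated.

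The cost is a few sentences and no new data. The reported DCR will be somewhat lower, and counting toxicity exits as not controlled is a conservative choice that should be stated as such.

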### 12 COMPLIANCE WITH GOOD CLINICAL PRACTICE, ETHICAL CONSIDERATIONS AND INFORMED CONSENT

### 12.1 Institutional Review Board

The protocol, any protocol modifications, informed consent form that will be used, and, if applicable, the permission to use private health information must be approved by the Investigator's IRB or Independent Ethics committee (IEC) (compliant with federal regulations 21 CFR 56) before the study is initiated. Documentation of this approval (i.e., a copy of the document showing IRB/IEC approval including the chairperson's signature and the date of approval) must be provided to Boston Biomedical or its designee, and made available during an inspection by the FDA, Health Canada or other regulatory agency inspectors. The Investigator will submit to Boston Biomedical:

- A list of the names, occupations, and affiliations of the members of the IRB
- Documentation that the IRB is duly constituted or a General Assurance Number
- No supplies will be shipped until the IRB has given written approval of the protocol and informed consent and Boston Biomedical has received copies of the approvals

It is the responsibility of the Investigator to:

- Submit to the IRB/IEC for review any advertisements that will be used to recruit subjects
- During the conduct of the study, submit progress reports to the IRB, if required, and request review of the study
- Report, in writing, to the IRB all SAEs that occurred during the study or SAEs reported in other studies using study drug, per local IRB regulations
- Inform the IRB of any changes in the protocol and obtain documented IRB approval of the changes
- Maintain a file of study-related information, including all correspondence with the IRB/IFC
- Within 3 months of study completion, provide the IRB with a final report on the study

### 12.2 Compliance with Good Clinical Practice and Ethical Considerations

This study must be conducted in compliance with IRB/IEC informed consent regulation and the ICH GCP Guidelines. In addition, all local regulatory requirements will be adhered to, in particular those which afford greater protection to the safety of the trial participants.

This study will be conducted according to the current revision of the Declaration of Helsinki (Revised Edinburgh, Scotland, 2000) and with local laws and regulations relevant to the use of new therapeutic agents in the country of conduct.

Before initiating a trial, the Investigator/institution should have written and dated approval/favorable opinion from the IRB/IEC for the trial protocol/amendment(s), written informed consent form, patient recruitment procedures (e.g., advertisements) and written information to be provided to patients.

Changes to the protocol will require written IRB/IEC approval/favorable opinion prior to implementation, except when the modification is needed to eliminate an immediate hazard(s) to patients.

### 12.3 Informed Consent and Permission to Use Private Health Information

The Investigator, or designee, is responsible for the content of the informed consent form, but the content must be submitted and approved by Boston Biomedical prior to submission to the IRB. Before the start of required study procedures, the Principal Investigator or associate must obtain informed consent from each study participant (or the subject's parent/guardian) in accordance with the US federal regulations (21 CFR Part 50) and ICH document "Guidance for Industry – E6 Good Clinical Practice: Consolidated Guidance" dated April 1996. It should also include any additional information required by local laws relating to institutional review.

Informed consent must be obtained from the subject before any screening activity, washout of medication, or treatment (that is not part of routine care) is undertaken. Informed consent will be obtained by discussing with the subject the purpose of the study, the risks and benefits, the study procedures, and any other information relevant to the subjects.

The subject or his/her legal representative will document their informed consent by signing the current version of the written, IRB-approved, informed consent form in the presence of a witness.

The person, who conducted the informed consent discussion with the subject and/or guardian, must also sign the informed consent form. The subject should be given a copy of the informed consent form with all of the appropriate signatures.

The Principal Investigator will ensure that a copy of the signed consent is kept with the Clinical Trial Master File.

The Investigator or designee must explain to the patient subject that for evaluation of study results, that subject's private health information obtained during the study may be shared with the study Sponsor, regulatory agencies, and ECs/IRBs, before enrolling that subject into the study. It is the Investigator's (or designee's) responsibility to obtain permission to use private health information per HIPAA from each subject, or if appropriate, the subject's parent or legal guardian.

### 13 STUDY MANAGEMENT

### 13.1 Amendments to the Protocol

Once the protocol has been approved by the IRB, the Investigator will not modify it without obtaining the prior concurrence of Boston Biomedical. In turn, Boston Biomedical will inform the Investigator in writing of any amendment to the protocol. The Investigator must submit the protocol modifications and any informed consent modifications to the IRB, and approval must be obtained before the modifications are implemented. Boston Biomedical will submit protocol modifications the FDA, and to Health Canada.

### 13.2 Investigator Brochure and Information Materials

Before the study begins, the Investigator will receive an Investigator's Brochure describing all known contraindications, warnings, precautions, and adverse reactions associated with the administration of the study drug. If such information is revised while the study is in progress,

the brochure will be amended or revised, and Boston Biomedical will provide the most current version to the Investigator.

### 13.3 Pre-investigational Documents

Prior to the shipment of the study drug(s), the Investigator will supply Boston Biomedical with the following:

- A signed Investigator Clinical Research Agreement
- A completed Form FDA 1572 signed by the Investigator
- Current curricula vitae and copy of current medical license for the Principal Investigator and Sub-Investigators listed on Form FDA 1572
- A completed financial disclosure form for all personnel listed on Form FDA 1572
- Signed and dated protocol signature page by the Principal Investigator
- A copy of the approval for this protocol from the IRB listed on Form FDA 1572
- A copy of the approval for the informed consent from the IRB listed on Form FDA 1572
- A copy of the IRB-approved informed consent
- Evidence of laboratory certification and a list of laboratory normal ranges for all laboratories listed on Form FDA 1572
- A list of the IRB members (listed on Form FDA 1572) and the member occupations and affiliations; written verification that the IRB is duly constituted or the General Assurance Number

### 13.4 Drug Inventory Record

The Investigator, or a responsible party (research pharmacist or other) designated by the Investigator, must maintain an inventory record of drug received and dispensed. Boston Biomedical will provide forms to facilitate the inventory control. These forms must be used unless the Investigator has previously established a system that complies with FDA and/or Health Canada regulations and is approved by Boston Biomedical. The study drug must be dispensed only to the institutions(s) specified on form FDA 1572.

### 13.5 Disposition of Used and Unused Study Drug

Upon completion or termination of the study and after inventory by a Boston Biomedical monitor or designated representative, all unopened drug is to be returned to Boston Biomedical in the original containers. All used vials will be retained until released for destruction by the Boston Biomedical monitor. Unopened returned drug, with completed Boston Biomedical forms for return shipment, should be shipped as instructed by the Sponsor.

### 13.6 Study Records

Boston Biomedical will provide the Investigator with drug shipment records, CRFs designed to collect the data specified for each individual, and other forms as necessary.

The Investigator and/or institution is required to prepare and maintain these forms in accordance with federal regulations (set forth in the Statement of Investigator Form FDA-1572) and to sign, date, and return them to the Sponsor.

Upon the request of authorized Boston Biomedical or appropriate regulatory agency personnel, the Investigator will make available for inspection subject source documents, e.g., records of each subject who participates in this study. This information will be treated as confidential.

### 13.7 Record Retention

Records must be maintained for 25 years:

If the Investigator leaves the institution where the study was conducted, he/she agrees that the records will be retained and will not be destroyed without prior notification of Boston Biomedical.

Boston Biomedical will notify the Investigator when records are no longer required.

